8.5 Safety Analysis

The overall safety profile of study drug will be assessed in terms of the following safety and tolerability endpoints:

- Adverse events
- Clinical laboratory values (hematology, chemistry, coagulation, and urinalysis)
- Standard 12-lead electrocardiograms
- Vital signs
- Pulse oximetry

Safety endpoints will be analyzed based on the Safety Set. Only a descriptive analysis of safety will be performed. Safety results for treatment groups in Part 2 Cohort 2A and Part 2 Cohort 2B will be presented separately, and overall.

For Part 2, the Safety Set refers to the Safety Set for the Treatment Period.

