^u FSH will be measured for any suspected postmenopausal female subjects with at least 12 months of continuous spontaneous amenorrhea.

^v A single blood sample will be collected for the G6PD activity test.

█ [Redacted]

^x On Days 3, 5, and 11, the following parameters will be measured: lactate dehydrogenase, total and direct bilirubin, alkaline phosphatase, aspartate aminotransferase, alanine aminotransferase, and gamma glutamyl transferase.

^y Blood samples will be collected for PK analysis of VX-152, VX-661, M1-661, IVA, and M1-IVA. On Day 1, samples will be collected before dosing (0 hours) and at 1, 2, 4, and 6 hours after dosing (relative to morning dose). On Day 8, a predose sample will be collected before the morning dose of study drug (0 hours). On Day 15, samples will be collected before dosing (0 hours) and at 1, 2, 4, 6, and 8 hours after dosing. At ETT Visits, a single blood sample for PK analysis will only be collected from subjects who discontinued study drug after Day 1, but before Day 15 PK was collected.

^z The last dose of VX-661/IVA will be the morning dose on Day 29.

Table 3-2 Study VX16-152-102: Schedule of Assessments for Part 2, Cohort 2A

Event/Assessment ^a	Screening	Run-in Period		Treatment Period ^b					Washout Period	ETT Visit ^c	Safety Follow-up 28 (± 7) Days After Last Dose ^d
	Days -56 to -29 ^e	Day -28 (± 1 day)	Day -14 ^f (± 1 day)	Day 1	Days 3 and 5 ^g (or Days 4/6 or Days 3/6) ^h	Day 8 (± 1 day)	Day 11 ^g (± 1 day)	Day 15 (± 1 day)	Day 29 (± 3 days)		
VX-152 or placebo dosing ^{aa}				Day 1 through Day 15							
AEs, medications ^{bb} , treatments and procedures	Continuous from signing of the ICF through the Safety Follow-up Visit										

^{aa} The last dose of VX-152 or placebo will be the morning dose on Day 15.

^{bb} Refer to [Section 9.4](#) for details.

Table 3-3 Study VX16-152-102: Schedule of Assessments for Part 2, Cohort 2B

Event/Assessment ^a	Screening	Run-in Period		Treatment Period ^b					Washout Period	ETT Visit ^c	Safety Follow-up 28 (± 7) Days After Last Dose ^d
	Days -56 to -29 ^e	Day -28 (± 1 day)	Day -14 ^f (± 1 day)	Day 1	Days 3 and 5 ^g (or Days 4/6 or Days 3/6) ^h	Day 8 (± 1 day)	Day 11 ^g (± 1 day)	Day 15 and Day 29 (± 1 day)	Day 43 (± 3 days)		
Informed consent	X										
Randomization ⁱ				X							
Demographics	X										
Medical history	X										
Ophthalmological history	X										
CFQ-R ^{j,k}				X		X		X	X	X ^l	X

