AEs, medications ^{bb} , treatments and procedures	Continuous from signing of the ICF through the Safety Follow-up Visit									

study drug (0 hours). On Day 15, samples will be collected before dosing (0 hours) and at 1, 2, 4, 6, and 8 hours after dosing. On Day 29, a sample will be collected before the morning dose (0 hours). At ETT Visits, a single blood sample for PK analysis will only be collected from subjects who discontinued study drug after Day 1, but before Day 29.

^z The last dose of VX-661/IVA will be the morning dose on Day 43.

^{aa} The last dose of VX-152 or placebo will be the morning dose on Day 29.

^{bb} Refer to [Section 9.4](#) for details.

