12.3.3.2 Analysis of Secondary Efficacy Variables

The secondary efficacy variables include:

- Absolute change from baseline for ppFEV₁ through Day 29 (Part 2, Cohort 2B only).
- Relative change in ppFEV₁ from baseline at Day 15 (Part 1 and Part 2), and through Day 29 (Part 2, Cohort 2B only)
- Absolute change in the CFQ-R respiratory domain score from baseline at Day 15 (Part 1 and Part 2), and at Day 29 (Part 2, Cohort 2B only)

Details of the analysis will be provided in the SAP.

The overall safety profile of study drug will be assessed based on the following safety and tolerability endpoints:

- Treatment-emergent adverse events (TEAEs)
- Clinical laboratory values (i.e., hematology, serum chemistry, coagulation, and urinalysis)
- ECGs
- Vital signs
- Pulse oximetry

All safety data will be summarized by treatment group and overall, for each Part. In addition, safety data will also be summarized separately for Part 2, Cohort 2B.

All safety data will be presented in individual subject data listings.

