7.3 Safety Set

 Part 1:

The **Safety Set** will include all subjects who received at least 1 dose of study drug. The Safety Set will be used for all safety analyses, unless otherwise specified.

If a subject received at least 1 dose of the higher VX-152 dose, then the subject will be analyzed in the treatment group with the highest VX-152 dose in the order of triple placebo,

VX-152 100mg + VX-661/IVA, VX-152 200mg + VX-661/IVA, and VX-152 300mg + VX-661/IVA.

 Part 2:

The **Safety Set for the Run-in Period** will include all subjects who received at least 1 dose of study drug in the Run-in Period. This Safety Set will be used for individual subject data listings for the Run-in Period, unless specified otherwise.

The **Safety Set for the Treatment Period** will include all subjects who received at least 1 dose of study drug in the Treatment Period. This Safety Set will be used for all safety analyses for the Treatment Period, unless specified otherwise.

If a subject received at least 1 dose of the higher VX-152 dose, then the subject will be analyzed in the treatment group with the highest VX-152 dose in the order of placebo + TEZ/IVA, VX-152 200mg + VX-661/IVA, and VX-152 300mg + VX-661/IVA.

The safety analysis will focus on the Safety Set for the Treatment Period only, unless otherwise specified.

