8 STATISTICAL ANALYSIS

8.1 General Considerations

The analysis will be performed for each part, and presented by treatment group, unless specified otherwise. The treatment groups are defined as follows:

- Part 1: *F508del*/MF genotype group
 - VX-152 100mg q12h + VX-661/IVA, VX-152 200mg q12h + VX-661/IVA, VX-152 300mg q12h + VX-661/IVA, and placebo, with VX-661 component administered as 100 mg qd and IVA component administered as 150 mg q12h.
- Part 2: *F508del/F508del* genotype group
 - VX-152 200mg q12h + VX-661/IVA, VX-152 300mg q12h + VX-661/IVA, VX-661/IVA, VX-661/IVA, VX-661/IVA from Cohort 2A and VX-661/IVA from Cohort 2B, with VX-661 component administered as 100 mg qd and IVA component administered as 150 mg q12h.

The Schedule of Assessments is provided in Appendix A. The precision standards for reporting safety and efficacy variables are provided in an internal Biometrics document that specifies the programming rules including the precision for derived variables.

All individual subject data for those randomized or dosed with any amount of study drug will be presented in data listings.

Continuous variables will be summarized using the following descriptive summary statistics: the number of subjects (n), mean, SD, standard error (SE), median, minimum value (min), and maximum value (max). SE may not be reported for safety summary tables.

Categorical variables will be summarized using counts and percentages. Percentages will be presented to 1 decimal place.

Baseline value, unless otherwise specified, will be defined as the most recent non-missing measurement (scheduled or unscheduled) collected before the first dose of study drug on Day 1 of the Treatment Period. For ECG, baseline will be defined as the most recent non-missing measurement (or the average of triplicate measurements, if the most recent non-missing measurement is obtained in triplicate), before the first dose of study drug on Day 1 of the Treatment Period.

Absolute change from baseline will be calculated as postbaseline value – baseline value.

Relative change from baseline will be calculated as (postbaseline value – baseline value)/baseline value.

Treatment-emergent (TE) period for Part 1 will include the time from the first dose of study drug in the Treatment Period to the Safety Follow-up (SFU) Visit, or 28 Days after the last dose of study drug for subjects who do not complete the SFU Visit.

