For Part 2, the TE period will be defined separately for the Run-In Period, and the Treatment Period:

- The TE period for the Run-in Period will include the time from the first dose of study drug in the Run-in Period to: (1) the last day prior to the first dose of study drug in the Treatment Period for subjects who complete the Run-in Period and continue to the Treatment Period, or (2) the SFU Visit for subjects who did not continue to the Treatment Period and have an SFU Visit, or (3) 28 days after the last dose of study drug in the Run-in Period for subjects who do not have an SFU Visit (e.g., subjects who do not meet the criteria to enter the Treatment Period and re-enter Study 661-110). Only data collected up to the end of study for a subject will be included in analysis.
- The TE period for the Treatment Period will include the first dose of study drug in the Treatment Period to: (1) the SFU Visit, or (2) 28 days after the last dose of study drug for subjects who do not have an SFU Visit (e.g. subjects whose Early Treatment Termination (ETT) Visit occurs 3 weeks or later following the last dose of study drug and the ETT visit replaces the SFU visit, or who leave the study early and re-enter Study 661-110). Only data collected up to the end of study for a subject will be included in analysis.

Unscheduled visits: Unscheduled visit measurements will be included in analysis as follows:

- In scheduled visit windows per specified visit windowing rules.
- In the derivation of baseline/last on-treatment measurements.
- In the derivation of maximum/minimum on-treatment values and maximum/minimum change from baseline values for safety analyses.
- In individual subject data listings as appropriate.

Visit windowing rules: The analysis visit windows for protocol-defined visits are provided in Appendix B.

Spirometry ($ppFEV_1$) will be used for both efficacy and safety purposes. For efficacy analysis, the assessments will follow the visit windowing rules for efficacy. For safety analysis, the assessments at 5 hours post-dose on nominal days 1 and 15 will be used.

Incomplete/missing data will not be imputed, unless specified otherwise.

Outliers: No formal statistical analyses will be performed to detect or remedy the presence of statistical outliers, unless specified otherwise.

Multiplicity: There will be no multiplicity adjustment for performing multiple hypothesis tests, unless specified otherwise.

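### In any by-Part or overall Part 2 safety display, 200 mg (Cohort 2A) and 300 mg (Cohort 2B) are shown over unequal windows, so dose is confounded with length of observation

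*SAP*

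**What the plan says.** **Display.** SAP 8.5 states: "Safety results for treatment groups in Part 2 Cohort 2A and Part 2 Cohort 2B will be presented separately, and overall". The protocol's safety analysis text (Section 12.3.5 in its table of contents) states: "All safety data will be summarized by treatment group and overall, for each Part", and adds that "safety data will also be summarized separately for Part 2, Cohort 2B". SAP 8.5.2 to 8.5.5 repeat the by-part wording for the threshold and oxygen-saturation summaries.

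**Windows.** SAP 8.1 says that the Part 2 TE period for the Treatment Period "will include the first dose of study drug in the Treatment Period to: (1) the SFU Visit", or 28 days after the last dose where there is no such visit, using only data up to the subject's end of study. SAP Appendix B puts Safety Follow-up at target Day 57 in Cohort 2A and Day 71 in Cohort 2B.

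**VX-152 dosing.** For 2A, protocol Table 3-2 says: "The last dose of VX-152 or placebo will be the morning dose on Day 15". For 2B, Table 3-3 says: "The last dose of VX-152 or placebo will be the morning dose on Day 29".

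**Comparator.** SAP 8.1 lists "VX-661/IVA from Cohort 2A and VX-661/IVA from Cohort 2B" among the treatment groups, next to repeated entries for VX-661/IVA with no cohort named. The as-treated rule in SAP 7.3 ranks Part 2 groups "in the order of placebo + TEZ/IVA, VX-152 200mg + VX-661/IVA, and VX-152 300mg + VX-661/IVA", with one comparator label. SAP 8.3 keeps comparators of different durations apart, but for efficacy analyses only.

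**Metric.** SAP 8.5.1 reports TEAEs as the number and percentage of subjects with an event. No time-adjusted or common-window AE summary is planned.

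**The concern.** As planned, each Part 2 dose is given in one cohort only, and the cohorts differ in both VX-152 duration and length of follow-up. A percentage of subjects who ever had an event, or ever crossed a threshold, rises with the time available even at a constant hazard. In a table with 200 mg and 300 mg in adjacent columns, the longer window pushes the 300 mg figure up whether or not dose matters.

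Safety is the primary objective and its analysis is descriptive, so no planned test or interval would temper a reader's impression of a dose gradient. The plan handles unequal duration explicitly for efficacy in SAP 8.3 but says nothing equivalent in SAP 8.5.

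**Working it through.** **1. The plan's own figure.** Protocol Table 12-1 (SAP Table 6-1) gives the chance of seeing at least one AE as 1 − (1 − p)^n. For n = 9 and 18 this returns 37.0% and 60.3% at p = 5%, 61.3% and 85.0% at 10%, and 76.8% and 94.6% at 15%. All six stated cells are reproduced. The footnote applies the same incidences to 2 weeks of treatment in groups of 9 and to 4 weeks in Cohort 2B, so the table does not show how incidence grows with duration.

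**2. Windows.**

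| | 2A (200 mg) | 2B (300 mg) | Ratio |
|---|---|---|---|
| Days on VX-152 or placebo | 15 | 29 | 1.93 |
| Last VX-661/IVA dose | Day 29 | Day 43 | |
| Safety Follow-up target (+28 days) | Day 57 | Day 71 | 1.25 |
| Planned TC / comparator subjects | 9 / 3 | 18 / 6 | |

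Within a cohort, TC and comparator have the same planned window, so length of observation adds nothing to that contrast.

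**3. Effect of window length alone.** Assume the same constant hazard in both cohorts. Then p(2B) = 1 − (1 − p(2A))^(T2B/T2A). The starting percentages are illustrative.

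- Events arising only on VX-152: 10% over 15 days gives 1 − 0.90^(29/15) = 18.4% over 29 days, a shift of 8.4 points.
- Background events: 30% by Day 57 gives 1 − 0.70^(71/57) = 35.9% by Day 71, a shift of 5.9 points. Starting values of 10% and 50% give 12.3% and 57.8%.
- Completers who re-enter Study 661-110 without a follow-up visit have windows of about 29 v 43 days. Here 10% becomes 1 − 0.90^(43/29) = 14.5%.

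**4. Sampling noise.** The standard error of the difference with 9 v 18 TC subjects is:

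- 10% v 18.4%: √(0.10 × 0.90/9 + 0.184 × 0.816/18) = 13.5 points.
- 30% v 35.9%: √(0.30 × 0.70/9 + 0.359 × 0.641/18) = 19.0 points.

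**5. Only if the comparators were merged.** Three subjects from 2A and six from 2B would have a mean window of (3 × 57 + 6 × 71)/9 = 66.3 days. A background 30% by Day 57 would then read 30.0% (200 mg), 35.9% (300 mg) and (3 × 30.0 + 6 × 35.9)/9 = 33.9% (VX-661/IVA) with no drug effect. Neither document says that this merging will be done for safety.

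**The case against.** The main safeguard is already in the plan. SAP 8.5 commits to cohort-separate results and SAP 8.1 names cohort-specific comparators, so each TC group is shown against its own randomised control over the same planned window. **This stands**, and it limits the point to displays that combine cohorts.

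A reader might infer that VX-661/IVA subjects are pooled across cohorts for safety, which would flatter 200 mg. The documents do not establish that. The single label in SAP 7.3 belongs to a rule for assigning subjects who received a higher dose; it does not define table columns. The repeated VX-661/IVA entries in SAP 8.1 may be a typing or extraction fault. What remains is an ambiguity in how the overall display treats the comparator.

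Nor does the plan say that Part 2 exists to compare doses. Protocol 8.2.2 gives additional safety data as the reason for four weeks in 2B. Part 1 gives all three doses for the same two weeks, though in another genotype. More cumulative events on a longer regimen are also partly a true property of that regimen.

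The by-visit laboratory, ECG, vital-sign and oximetry summaries compare like days and are unaffected. The shifts are also well below one standard error. Noise does not remove a bias of known direction that recurs across the cumulative tables, but it does rule out calling the effect large.

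**Conclusion.** The point holds for by-Part or overall Part 2 displays of cumulative summaries: TEAE percentages, threshold criteria and lowest oxygen saturation. In these, 200 mg v 300 mg is confounded with 15 v 29 days on VX-152 and 57 v 71 days of planned TE follow-up. The illustrative shifts are 8.4 points for on-drug events (10% to 18.4%) and 5.9 points for background events (30% to 35.9%), against standard errors of 13.5 and 19.0 points.

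These figures rest on a constant, equal hazard, chosen starting incidences, planned cohort sizes, doses as planned and, for 57 v 71 days, follow-up visits on target. They show direction and rough size and do not forecast the result.

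It would go too far to say that Part 2 has no like-for-like safety comparison, or that a merged comparator will make 200 mg look safer than VX-661/IVA. The first is contradicted by SAP 8.5 and the second is not stated anywhere. No planned test depends on this point. It is a worthwhile, inexpensive improvement to how the primary objective is reported.

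**What to change.** In SAP 8.5 and 8.5.1, for Part 2:

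1. For any display that combines cohorts, add a TEAE overview and a threshold summary restricted to the period from the first VX-152 or placebo dose through Day 15, where the 2A and 2B schedules match. Alternatively, report events per patient-week of TE observation beside the percentages. The patient-weeks already planned in SAP 8.2.4 measure study-drug exposure (the whole drug period, or Treatment plus Washout), so they are not the right denominator as they stand.
2. For the full TE period, keep the VX-661/IVA groups separate by cohort, as SAP 8.3 does for efficacy. Say so explicitly, so that the meaning of the overall display is settled.
3. Footnote the full-period tables to say that 200 mg v 300 mg percentages are not a dose comparison.

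The cost is SAP wording and a few extra tables from data already collected, with no change to conduct or sample size. The Day 15 cut omits later events, but these stay in the full-period tables.

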8.5.1 Adverse Events

AEs will be classified as pretreatment AEs, TEAEs, or post-treatment AEs, defined as follows:

For Part 1:

Pretreatment AE: any AE that started before the first dose date of study drug

TEAE: any AE that worsened (either in severity or seriousness) or that was newly developed at or after the first dose date of study drug through the end of the TE period

Post-treatment AE: any AE that worsened (either in severity or seriousness) or that was newly developed beyond the TE period

For Part 2:

Pretreatment AE: any AE that started before the first dose date of study drug

TEAE during the Run-in Period: any AE that worsened (either in severity or seriousness) or that was newly developed at or after the first dose date of study drug through the end of the TE period for the Run-in Period

TEAE during the Treatment Period: any AE that worsened (either in severity or seriousness) or that was newly developed at or after the first dose date of study drug through the end of the TE period for the Treatment Period

Post-treatment AE: any AE that worsened (either in severity or seriousness) or that was newly developed beyond the TE period

For AEs with completely missing or partially missing start dates, if there is no clear evidence that the AEs started before or after study treatment, the AEs will be classified as TEAEs.

Details for imputing missing or partial start dates of adverse events are described in Appendix G.

An adverse event overview table will be provided for the TE period (TE period for the Treatment Period for Part 2) by treatment group, for the following:

- Number of TEAEs (total number of TEAEs only)
- Subjects with any TEAEs
- Subjects with TEAEs by Strongest Relationship
- Subjects with TEAEs by Maximum Severity
- Subjects with TEAEs Leading to Treatment Discontinuation
- Subjects with TEAEs Leading to Drug Interruption
- Subjects with Serious TEAEs
- Subjects with TEAE Leading to Death

Summaries will be presented by MedDRA system organ class (SOC) and preferred term (PT) using frequency counts and percentages (i.e., number and percentage of subjects with an event). When summarizing the number and percentages of subjects, subjects with multiple occurrences of the same adverse event or a continuing adverse event will be counted once, and only the maximum severity level will be presented in the severity summaries, and the strongest relationship level in the relationship summaries.

All AEs, including pre-treatment AEs, TEAEs for all applicable periods, and post-treatment AEs, will be presented in an individual subject data listing based on the All Subjects Set. Subjects who enrolled from Study 661-110 will be identified in the listing based on the subject ID.

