8.1.2 Run-in Period (Part 2)

The Run-in Period will have a total duration of 4 weeks and is designed to establish a reliable on-treatment (VX-661/IVA) baseline for the Treatment Period. The first dose of VX-661/IVA will be administered at the Day -28 Visit. The last dose of VX-661/IVA within the Run-in Period will be administered in the evening of Day -1 (1 day before the Day 1 Visit).

Study eligibility for Part 2 subjects will be confirmed before the first dose of VX-661/IVA in the Run-in Period (on Day -28).

Study visits during the Run-in Period will occur as shown in [Table 3-2](#) and [Table 3-3](#). All visits will occur within the windows specified.

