9.2 Exclusion Criteria

1. History of any comorbidity that, in the opinion of the investigator, might confound the results of the study or pose an additional risk in administering study drug to the subject.
2. History of cirrhosis with portal hypertension.

3. Risk factors for Torsade de Pointes, including but not limited to, history of any of the following: familial long QT syndrome, chronic hypokalemia, heart failure, left ventricular hypertrophy, chronic bradycardia, myocardial infarction, cardiomyopathy, history of arrhythmia (ventricular or atrial fibrillation), obesity, acute neurologic events (subarachnoid hemorrhage, intracranial hemorrhage, cerebrovascular accident, or intracranial trauma), or autonomic neuropathy.
4. History of hemolysis.
5. G6PD deficiency, defined as G6PD activity less than the lower limit of normal (LLN) or 70% of the mean of the LLN and the ULN, whichever is greater.
6. Any of the following abnormal laboratory values at screening:
 - Hemoglobin <10 g/dL
 - Total bilirubin $\geq 2 \times$ ULN
 - AST, ALT, gamma-glutamyl transpeptidase (GGT), or alkaline phosphatase (ALP) $\geq 3 \times$ ULN
 - Abnormal renal function defined as glomerular filtration rate ≤ 50 mL/min/1.73 m² (calculated by the Modification of Diet in Renal Disease Study Equation)^{10,11} for subjects ≥ 18 years of age
7. An acute upper or lower respiratory infection, pulmonary exacerbation, or changes in therapy (including antibiotics) for pulmonary disease within 28 days before the first dose of study drug (Day 1 for Part 1, Day -28 for Part 2).
8. Lung infection with organisms associated with a more rapid decline in pulmonary status (e.g., *Burkholderia cenocepacia*, *Burkholderia dolosa*, and *Mycobacterium abscessus*). For subjects who have had a history of a positive culture in the past, the investigator will apply the following criteria to establish whether the subject is free of infection with such organisms:
 - The subject has had 2 respiratory tract cultures negative for these organisms within the past 12 months, with no subsequent positive cultures.
 - These 2 respiratory tract cultures were separated by at least 3 months, and 1 of them was obtained within the past 6 months.
9. An acute illness not related to CF (e.g., gastroenteritis) within 14 days before the first dose of study drug (Day 1 for Part 1, Day -28 for Part 2).

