10 STUDY DRUG ADMINISTRATION AND MANAGEMENT

Study drug refers to VX-152, VX-661/IVA, IVA, and their matching placebos.

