12.3.5.1 Adverse Events

For analysis purposes, AEs will be classified as pretreatment AEs, TEAEs, or post-treatment AEs, defined as follows:

- Pretreatment AE: any AE that started before the first dose of study drug
- TEAE: any AE that increased in severity or that was newly developed at or after the first dose of study drug through the end of the TE Period
- Post-treatment AE: any AE that increased in severity or that was newly developed beyond the TE Period

For AEs with missing or partial start dates, if there is no clear evidence that the AEs started before or after study drug treatment, then the AEs will be classified as TEAEs.

AE summary tables will be presented for TEAEs only, overall and by treatment group for each Part, and will include the following:

- All TEAEs
- TEAEs by strongest relationship
- TEAEs by maximum severity
- TEAEs leading to treatment discontinuation
- Serious TEAEs
- TEAEs leading to death
- Frequently reported TEAEs

Summaries will be presented by MedDRA system organ class and preferred term using frequency counts and percentages (i.e., number and percentage of subjects with an event). When summarizing the number and percentage of subjects with an event, subjects with multiple occurrences of the same AE or a continuing AE will be counted once, only the maximum severity level will be presented in the severity summaries, and the strongest

relationship level in the relationship summaries. In addition, a listing containing individual subject level AE data for all deaths and other serious and significant AEs will be provided separately. All AEs, including pre- and post-treatment AEs, will be presented in individual subject data listings.

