8.2.3 Prior and Concomitant Medications

Medications used in this study will be coded by using the World Health Organization Drug Dictionary Enhanced (WHO-DDE) and categorized as the following:

For Part 1:

Prior medication: any medication that started before the first dose date of study drug, regardless of when the medication ended.

Concomitant medication: medication continued or newly received on or after the first dose date of study drug through the end of the TE period.

Post-treatment medication: medication continued or newly received after the TE period.

For Part 2:

Prior medication: any medication that started before the first dose date of study drug in the Run-in Period, regardless of when the medication ended.

Concomitant medication during the Run-in Period: medication continued or newly received on or after the first dose date of study drug during the Run-in Period through the end of TE period for the Run-in Period.

Concomitant medication during the Treatment Period: medication continued or newly received on or after the first dose date of study drug during the Treatment Period through the end of TE period for the Treatment Period.

Post-treatment medication: medication continued or newly received after the TE period.

A given medication may be classified as follows: prior, concomitant, post-treatment, both prior and concomitant, both concomitant and post-treatment, or prior, concomitant, and post-treatment. Concomitant for Part 2 can be concomitant during the Run-in Period, concomitant during the Treatment Period, or both.

If a medication has a completely missing or partially missing start/stop date and it cannot be determined whether it was taken before the first dose date of study drug, concomitantly, or after the TE period, it will be classified as prior, concomitant, and post-treatment.

Prior medications and concomitant medications will be summarized descriptively using frequency tables by preferred name.

Summaries of medications will be based on the FAS, and presented by treatment group and overall for each part.

Post-treatment medications will be listed only.

Details for imputing missing or partial start and/or stop dates of medication are described in Appendix C.

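### In Part 2, SAP 8.5.1 starts the Treatment Period TEAE window at an unqualified first dose of study drug (Day -28), which contradicts the Treatment Period start in SAP 8.1

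*SAP*

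**What the plan says.** SAP 8.5.1 gives Part 2 separate TEAE classes for the Run-in Period and the Treatment Period. The run-in class covers events that are new or worsen "at or after the first dose date of study drug through the end of the TE period for the Run-in Period". The Treatment Period class covers those "at or after the first dose date of study drug through the end of the TE period for the Treatment Period". The two definitions start identically and differ only in where they end. The pretreatment class uses the same unqualified first dose date.

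The protocol fixes what that date is in Part 2. Section 10 states: "Study drug refers to VX-152, VX-661/IVA, IVA, and their matching placebos". Section 8.1.2 states: "The first dose of VX-661/IVA will be administered at the Day -28 Visit". Exclusion criteria 7 and 9 in section 9.2 spell out the "first dose of study drug (Day 1 for Part 1, Day -28 for Part 2").

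Other sections name the period. SAP 8.1 says that the TE period for the Treatment Period "will include the first dose of study drug in the Treatment Period to" the Safety Follow-up Visit, or to 28 days after the last dose if there is no such visit. SAP 8.2.3 counts as Treatment Period concomitant medication whatever is still being taken, or is started, "on or after the first dose date of study drug during the Treatment Period through the end of TE period for the Treatment Period". The protocol is mixed: section 12.3.1 starts the TE Period at the first dose in the Treatment Period, while section 12.3.5.1 defines a TEAE as one that worsened or was "newly developed at or after the first dose of study drug through the end of the TE Period".

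**The concern.** Protocol 12.1.1.1 and SAP 6.2.1.1 name AE incidence as the primary safety endpoint, so the TEAE definition decides which events enter the main safety tables. During the run-in every Part 2 subject takes VX-661/IVA, and nobody is randomized until Day -1 or Day 1. Events from that time carry no information about VX-152. If they entered the Treatment Period tables by treatment group, they would add background events to both arms and could create a chance imbalance between them. The comparator groups are very small (3 subjects in Cohort 2A, 6 in Cohort 2B), so a single misplaced event is visible in the percentages.

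There is also a consistency issue. SAP 8.5.2 and 8.5.3 tie the laboratory and ECG threshold tables to the Treatment Period TE period. AE tables programmed from the literal 8.5.1 sentence would use a different window from the rest of the safety output.

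**Working it through.** The plan states no figure to reproduce here. The check compares the texts and then counts nominal days.

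**Step 1: the start date under the literal 8.5.1 wording.** Study drug includes VX-661/IVA (protocol 10), and VX-661/IVA begins on Day -28 (protocol 8.1.2). The protocol itself equates the Part 2 first dose of study drug with Day -28 (protocol 9.2). In the pretreatment and run-in definitions the phrase can only mean Day -28. Read the same way in the next definition of the same list, it gives the Treatment Period class a Day -28 start too.

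**Step 2: a test case.** Take a subject who continues to randomization and has a new AE on Day -20, with a complete start date.
- 8.5.1, run-in definition: after Day -28 and before the run-in TE period ends, so it qualifies.
- 8.5.1, Treatment Period definition, literal: after Day -28 and before the Treatment Period TE period ends, so it also qualifies.
- 8.1: the run-in TE period ends the day before the first Treatment Period dose, and the next TE period starts at that dose. The event belongs to the run-in only.

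The two sections therefore give different flags for the same event. An event that starts in the run-in and worsens after Day 1 is a Treatment Period TEAE under both readings and is not in dispute.

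**Step 3: the length of the two windows.** Inputs: run-in Day -28 to Day -1 = 28 days, with no Day 0. The last VX-661/IVA dose is on Day 29 in Cohort 2A and Day 43 in Cohort 2B (protocol Tables 3-2 and 3-3). Follow-up comes 28 days later, so Day 29 + 28 = Day 57 and Day 43 + 28 = Day 71, which agree with the target days in SAP Appendix B.
- Cohort 2A: 8.1 window 57 days; literal window 28 + 57 = 85 days; pre-Day 1 share 28/85 = 32.9%.
- Cohort 2B: 8.1 window 71 days; literal window 28 + 71 = 99 days; pre-Day 1 share 28/99 = 28.3%.

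**Step 4: the weight of one subject.** One subject counted only because of a run-in event moves the group percentage by 1/N.
- Comparator: 1/3 = 33.3 points (2A); 1/6 = 16.7 points (2B).
- Triple combination: 1/9 = 11.1 points (2A); 1/18 = 5.6 points (2B).

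**Step 5: with the period named.** If the Treatment Period definition starts at the first dose in that period, the windows are Day 1 to Day 57 and Day 1 to Day 71. These match SAP 8.1 and contain no run-in days.

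**The case against.** The strongest reply is that the plan, read as a whole, already excludes run-in events. SAP 8.1 makes the two TE periods disjoint for subjects who continue. The 8.5.1 sentence on the overview table says that in Part 2 the table covers the Treatment Period TE period. Appendix G.2 sorts imputed AE start dates by comparison with the TE period. When the start year is missing, it classes an event that ended after run-in dosing began but before Treatment Period dosing as a run-in TEAE. Protocol 12.3.1 agrees, and the label of the class itself points to the Treatment Period. Safety is descriptive only, and the AE listing shows TEAEs for all applicable periods, so run-in events would remain visible.

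Most of this stands. It shows that the drafters did not intend to include run-in events. A reader might infer that the plan does count them as Treatment Period TEAEs and so inflates both arms; the documents do not support that, because it would follow only if a programmer applied one sentence and ignored the others.

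The reply does not repair the sentence, however. SAP 8.1 defines a period, and 8.5.1 uses that period only for the end of its window. The period is named for the overview table, but the sentence on summaries by system organ class and preferred term names none. Appendix G covers only missing or partial dates, so an event with a complete date is classified by 8.5.1. The protocol has the same gap between 12.3.1 and 12.3.5.1.

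**Conclusion.** SAP 8.5.1 is wrong as written for Part 2 and contradicts SAP 8.1. The qualifier present in the parallel medication definition in 8.2.3 suggests a drafting omission. The consequence is a risk that TEAE flags are misprogrammed or that run-in events are counted twice; no analysis choice is in dispute.

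If the sentence were programmed literally, about a third of the nominal AE window in Cohort 2A (28 of 85 days) and just over a quarter in Cohort 2B (28 of 99 days) would precede Day 1. These are shares of nominal days and would be shares of events only at a constant AE rate, which is an assumption. The one-subject shifts of 33 and 17 points assume the planned comparator sizes.

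Two further inferences are tempting but unsupported. One is a larger share for subjects who re-enter Study 661-110, on the view that their window stops at the last study visit. Protocol 13.1.1.3 continues AE collection to 28 days after the last dose for enrolled subjects without a follow-up visit, unless a late early-termination visit ends it sooner. SAP 8.1 gives the same 28 days, limited to data up to the end of study, and sets no earlier date. The other is a specific rise in reported incidence, which would need a background AE rate that the documents do not give.

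**What to change.** In the Part 2 list in SAP 8.5.1:
- Treatment Period TEAE: add *in the Treatment Period* after the first dose date of study drug.
- Pretreatment AE and run-in TEAE: add *in the Run-in Period* at the same place.
- Add a cross-reference to the two TE periods in SAP 8.1, and state that it governs all Part 2 TEAE summaries, including those by system organ class and preferred term.

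The end of the run-in TEAE window needs no change, because SAP 8.1 already sets it. Align protocol 12.3.5.1 with protocol 12.3.1, so that both start at the first dose in the Treatment Period.

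The cost is a few words. No new data or assessments are needed, and SAP section 3 allows a documented amendment before the database lock for the final analysis. Any interim AE output already programmed should be checked against the SAP 8.1 windows.
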